1.5 Rationale

Metastatic castration resistant prostate cancer (CRPC) is an area of urgent unmet clinical need, especially in the clinical state characterized by resistance to or progression on monotherapy with androgen signaling inhibitors (ASI) such as abiraterone acetate and/or enzalutamide. In the CRPC setting, androgen receptor (AR) signaling continues to remain active and drives cancer progression. More potent inhibitors of AR-driven signaling, especially those that circumvent mechanisms of castration resistance involving the AR (e.g. AR splice variants or AR mutations), could help prolong the duration of benefit from ASI such as enzalutamide by avoiding or delaying development of resistance. We therefore propose a Phase Ib/II Single-Arm Multi-Center Study of IONIS-AR-2.5_{Rx}, the Androgen Receptor Antisense Oligonucleotide in combination with enzalutamide in Metastatic Castration Resistant Prostate Cancer.

1.6 Correlative Studies

IONIS-AR-2.5_{Rx} acts by targeting full length and all variants of AR mRNA by targeting them for degradation. AR mRNA levels and those of the AR mutant and variants are expected to be reduced upon treatment with IONIS-AR-2.5_{Rx}. We seek to determine the inhibition of androgen receptor driven signaling by IONIS-AR-2.5_{Rx} in tumor tissues. Secondly, we seek to identify other molecular (including genomic, metabolic, and/or proteomic) biomarkers in blood and tumor tissue potentially indicative of clinical response/resistance, safety, pharmacodynamic activity and/or the mechanism of action of IONIS-AR-2.5_{Rx} in combination with enzalutamide. We will explore pharmacokinetic (PK) characteristics of IONIS-AR-2.5_{Rx}. Finally, we will explore the quality of life impact of IONIS-AR-2.5_{Rx} in combination with enzalutamide.

2.0 STUDY OBJECTIVES/ENDPOINTS

2.1 Primary Objective

Phase Ib: To determine the maximum tolerated dose (MTD) of IONIS-AR-2.5_{Rx} in combination with enzalutamide.

Phase II: To estimate the anti-tumor efficacy of IONIS-AR-2.5_{Rx} in combination with enzalutamide as measured by PSA response rate in patients with metastatic castration resistant prostate cancer.

2.2 Secondary Objectives

- 2.2.1 To estimate secondary measures efficacy of IONIS-AR-2.5_{Rx} in combination with enzalutamide in CRPC subjects including radiographic progression-free survival (rPFS) by PCWG3-modified RECIST 1.1, 30% PSA reduction proportion, PSA progression-free survival, Duration of Therapy (DOT), Duration of Response (DOR), PFS and OS.
- 2.2.2 To determine the safety and toxicity of IONIS-AR-2.5_{Rx}, the Androgen Receptor AntiSense Oligonucleotide (AR ASO) in patients with metastatic castration resistant prostate cancer.

2.3 Exploratory/Correlative Objectives

- 2.3.1 To determine the inhibition of androgen receptor driven signaling by IONIS-AR-2.5_{Rx} in tumor tissues.
- 2.3.2 To identify molecular (including genomic, metabolic, and/or proteomic) biomarkers in blood and tissues that may be indicative of clinical response/resistance, safety, pharmacodynamic activity and/or the mechanism of action of IONIS-AR-2.5_{Rx} in combination with enzalutamide.
- 2.3.3 To evaluate changes in health-related quality of life assessment from baseline using FACT-P and EuroQoL-5D.
- 2.3.4 To explore pharmacokinetic (PK) characteristics of IONIS-AR-2.5_{Rx} in combination with enzalutamide.

2.4 Primary Endpoint

- 2.4.1 Dose-limiting toxicity (DLT) during the first cycle of IONIS-AR-2.5_{Rx} (in combination with enzalutamide)
- 2.4.2 PSA decline of 50% or greater from baseline using PCWG3 criteria at any time after the start of combination therapy

2.5 Secondary Endpoints

- 2.5.1 Efficacy: Radiographic progression-free survival time (rPFS) by PCWG3-modified RECIST 1.1, PSA reduction from baseline, PSA progression-free survival time, duration of therapy (DOT), duration of PSA Response (DOR), progression-free survival time and overall survival time
- 2.5.2 Safety and toxicity: Adverse events as assessed by CTCAE criteria 5.0 and classified by body system, grade and attribution. Other toxicity endpoints include intrapatient dose delays and dose reductions.

2.6 Exploratory/Correlative Endpoints

[figure not shown]
- 2.6.1 Androgen receptor driven signaling measures in tumor tissues
- 2.6.2 Measures of genomic metabolomics and proteomic biomarkers in blood and tissues
- 2.6.3 FACT-P and EuroQoL-5D scores with comparisons to baseline scores
- 2.6.4 Pharmacokinetic (PK) characteristics

3.0 PATIENT ELIGIBILITY

Subjects must meet all of the inclusion and exclusion criteria to be enrolled to the study. Study treatment may not begin until a subject is enrolled. No eligibility waivers will be granted for this clinical trial.

3.1 Inclusion Criteria

- 3.1.1 Ability to understand and voluntarily agree to participate by providing written informed consent for the trial.
- 3.1.2 Histologically confirmed prostate adenocarcinoma cancer, either pure or mixed. Small cell/neuroendocrine differentiation is not allowed.
- 3.1.3 Castrate levels of serum testosterone (≤ 50 ng/dL). Patients must continue androgen deprivation therapy with an LHRH analogue or antagonist if they have not undergone bilateral orchectomy.
- 3.1.4 Patients must have metastatic disease; either non-measurable disease OR measurable disease per RECIST 1.1.
- 3.1.5 Progressive disease despite ongoing treatment with Androgen Deprivation Therapy (ADT) based **on ANY one of the following**:
 - 1) Progression on axial imaging per treating investigator
 - 2) PSA evidence for progressive prostate cancer consists of a PSA level of at least 1 ng/ml which has risen on at least 2 successive occasions, at least one week apart. If the confirmatory PSA (#3) value is less (i.e., #3b) than the screening PSA (#2) value, then an additional test for rising PSA (#4) will be required to document progression for the purposes of eligibility.

- 3) Radionuclide bone scan: At least two new foci consistent with metastatic lesions
- 3.1.6 Patients treated with first generation anti-androgen as most recent systemic therapy (e.g. bicalutamide, nilutamide) must have at least 4 weeks elapsed from treatment discontinuation to start of protocol therapy with evidence of disease progression per criterion 3.1.5 *following* discontinuation of prior anti-androgen.
- 3.1.7 Minimum PSA at entry of 1 ng/mL is required.
- 3.1.8 ECOG Performance Status 0,1 or 2
- 3.1.9 Be ≥ 18 years of age on the day of signing informed consent.
- 3.1.10 Demonstrate adequate organ function as defined below:

System	Laboratory Value
Hematological	
ANC	$\geq 1,500/\mu\text{L}$
Platelets	$\geq 100,000/\mu\text{L}$
Hemoglobin	$\geq 9 \text{ g/dL}$ or $\geq 5.6 \text{ mmol/L}$ with or without a red blood cell transfusion within 2 weeks of enrollment
Renal	
Serum creatinine OR calculated creatinine clearance (GFR can also be used in place of creatinine or CrCl)	$\leq 1.5 \times \text{ULN}$ OR $\geq 30 \text{ mL/min}$ for subjects with creatinine levels $>1.5 \times$ institutional ULN
Hepatic	
Serum total bilirubin	$\leq 1.5 \times \text{ULN}$ OR Direct bilirubin $\leq \text{ULN}$ for subjects with total bilirubin levels $>1.5 \text{ ULN}$
AST (SGOT) and ALT (SGPT)	$\leq 2.5 \times \text{ULN}$ OR $\leq 5 \times \text{ULN}$ for subjects with active liver metastases
Alkaline Phosphatase	If $>2.5 \times \text{ULN}$, then liver fraction should be $\leq 2.5 \times \text{ULN}$
Coagulation	
INR PT aPTT or PTT	$\leq 1.5 \times \text{ULN}$ This can vary if subject is receiving anticoagulant therapy, as long as PT or PTT remains within therapeutic range of the anticoagulant's intended use

3.1.11 Subjects must agree to use an adequate method of contraception as outlined in Section 8.1.1. starting with the time of informed consent through 120 days after the last dose of trial therapy.

3.2 Exclusion Criteria

3.2.1 Prior chemotherapy and/or enzalutamide for metastatic castration-resistant prostate cancer. Chemotherapy administered in the castration-sensitive setting is allowed provided last dose of chemotherapy was greater than 6 months prior to study entry.

3.2.2 Is currently participating and receiving study therapy or has participated in a study of an investigational agent and received study therapy or used an investigation device within 4 weeks of enrollment.

3.2.3 Has not recovered (i.e., AE \leq Grade 1 or at baseline) from AEs due to a previously administered agent. Subjects with \leq Grade 2 neuropathy or \leq Grade 2 alopecia are an exception to this criterion and are allowed if relevant toxicity is stabilized.

3.2.4 If subjects received major surgery they must have recovered adequately from the toxicity and/or complications from the intervention prior to starting trial therapy.

3.2.5 Has a known additional malignancy that is progressing or requires active treatment. Exceptions include basal cell carcinoma of the skin or squamous cell carcinoma of the skin.

- 3.2.6 Has known psychiatric or substance abuse disorders that would interfere with cooperation with the requirements of the trial. At the time of signing informed consent is a known regular user (including "recreational use") of any illicit drug(s) or had a recent history (within the last year) of drug or alcohol abuse.
- 3.2.7 Has a known history of human immunodeficiency virus (HIV) (HIV 1/2 antibodies).
- 3.2.8 Has known active hepatitis B (e.g., HBsAg reactive) or hepatitis C (e.g., HCV RNA [qualitative] is detected).
- 3.2.9 Has received a live virus vaccine within 30 days of planned start of trial therapy.
- 3.2.10 Has known active CNS metastases and/or carcinomatous meningitis. Subjects with previously treated brain metastases may participate provided they have stable brain metastases (stability is normally defined as a period of 1 to 3 months in which there is no evidence of new or enlarging CNS metastases).
- 3.2.11 Has symptomatic ascites or pleural effusion; a subject who is clinically stable following treatment for these conditions is eligible.
- 3.2.12 Has had a prior allogeneic stem cell or bone marrow transplant.
- 3.2.13 Has known contraindication to aspirin (81 mg).

4.0 SUBJECT SCREENING AND REGISTRATION PROCEDURES

Patient registration for this trial will be centrally managed by the Coordinating Center of the University of Michigan Rogel Cancer Center as described below:

A potential study subject who has been screened for the trial and who has signed the Informed Consent document will be initially documented by the participating site on the Screening and Enrollment Log provided by the Coordinating Center.

It is the responsibility of the local site investigator to determine patient eligibility prior to submitting patient registration request to the Coordinating Center. After patient eligibility has been determined, a copy of the completed Eligibility Worksheet together with all the pertinent de-identified source documents will be submitted by the requesting site to the Coordinating Center, by email to [contact].

The Multi-Site Coordinator, who acts as the registrar, will review the submitted documents and process the registration. Sites should inform the Multi-Site Coordinator of a potential registration by 5 p.m. on the day prior to registration. Same day registrations cannot be guaranteed.

An email will be sent by the registrar to the requesting site registrar to confirm patient registration and to provide the study identification number that has been assigned to the patient. In addition, a copy of the completed Eligibility Worksheet signed and dated by the registrar, will be sent back to the requesting site registrar.

Patients found to be ineligible for participation after being consented will be considered screen failures, and documented as such in the Screening and Enrollment Log. These patients will not have study identification number assigned to them, and will not receive study treatment.

5.0 TREATMENT PLAN

5.1 Treatment Dosage and Administration

Protocol treatment must start within 14 business days of enrollment to the study.

5.1.1 Overall Treatment Plan:

Phase Ib/II: All registered subjects will be treated with IONIS-AR-2.5_{Rx} (ASO) in combination with enzalutamide. IONIS-AR-2.5_{Rx} will be given intravenously in 60-minute infusions on Days 1, 4, 8, 11, 15 on cycle 1, then on days 1, 8, 15 in subsequent 21-day cycles. Enzalutamide will be taken daily in 21 day cycles starting Day 1 of cycle 1. Treatment will continue until clinical or radiologic progression or unacceptable toxicity. The infusion duration may be extended to 120 minutes for individuals experiencing infusion reactions.

- Baseline archival CRPC tumor tissue will be collected (mandatory) as well as tumor biopsies (optional) after 2 cycles of IONIS-AR-2.5_{Rx} and, tumor biopsies (optional) at progression.

Phase	Agent	Premedications; Precautions	Starting Dose	Route	Schedule
Phase Ib and II	IONIS-AR-2.5 _{Rx}	Per institutional standards for low emetogenic risk	Assigned Dose Level (See table in 5.1.2)	IV infusion over 60 minutes (+/-15 minutes)	*Days 1, 4, 8, 11 and 15 of cycle #1. *Days 1, 8, 15 of each subsequent 21-day cycle
Phase Ib and II	Enzalutamide	No premedications mandated but may be used at investigator discretion/institutional standards	160 mg Qday	Oral	Day 1-21 of each 21-day cycle

Starting on Cycle 1 Day 1, all subjects should take ASA 81 mg PO Qday unless contraindicated.

As noted in section 1.2, the primary study drug IONIS-AR-2.5_{Rx} has been associated with an increased risk of venous thromboembolism (VTE) in early clinical data. Prostate cancer is not associated with a high baseline incidence of VTE, and therefore routine VTE prophylaxis is not required in this patient population based on current NCCN guidelines for cancer-associated VTE. Low-dose aspirin for VTE prophylaxis has been recommended in multiple myeloma patients based on these NCCN guidelines (https://www.nccn.org/professionals/physician_gls/f_guidelines.asp). The overall likelihood of increased risk of VTE events with use of IONIS-AR-2.5_{Rx} in prostate cancer patients is unknown, but given the relatively increased rate of VTE events in the initial study population, VTE prophylaxis appears to be warranted in further clinical study populations.

Patients in the current phase II trial will receive low dose aspirin (81 mg) daily while receiving study drug to mitigate the apparent increased risk of VTE.

Clotting and bleeding functions including platelet counts will be closely monitored on this study including weekly CBCPD, PT/PTT/INR and reviewed continuously as well at the interim analysis time points. If so needed and indicated by the data, including at interim safety analysis and continually by the Data and Safety Monitoring Board, we would modify the above strategy towards either escalating the prophylactic anti-coagulation to enoxaparin 40 mg daily, for example, or removing the 81 mg daily dose of aspirin.

5.1.2 Upon enrollment, each patient will be assigned a dose level from the statistician to initiate treatment. (See Section 11 for further details.)

Assigned Dose level (TITE-CRM):

Assigned Dose Level	Enzalutamide Dose	IONIS-AR-2.5 _{Rx} Dose
3	160 mg	900 mg
2	160 mg	750 mg
1	160 mg	600 mg

5.1.3 Definition of Dose Limiting Toxicity (DLT):

Excessive toxicity/dose limiting toxicity (DLT) will be defined as any Grade 3 or higher toxicity (as defined by CTCAE v5.0) that occurs during the DLT evaluation period (2 cycles plus labs prior to start of cycle 3). Toxicity that is clearly and directly related to the primary disease or to another etiology is excluded from this definition. The following will be DLTs:

- Liver transaminase elevation Grade 2 lasting 14 calendar days or more OR Liver transaminase elevation Grade 3 or 4
- Grade 3 or Grade 4 febrile neutropenia will be a DLT regardless of duration or reversibility
- Grade 3 thrombocytopenia that IS associated with clinically significant bleeding that requires medical intervention

The DLT Definition excludes the following conditions:

- Grade 3 fatigue lasting ≤ 7 days
- Grade 3 endocrine disorder (thyroid, pituitary, and/or adrenal insufficiency) that is managed with or without systemic corticosteroid therapy and/or hormone replacement therapy and the subject is asymptomatic
- Grade 3 infusion-related reaction (first occurrence and in the absence of steroid prophylaxis) that resolves within 6 hours with appropriate clinical management
- Grade 3 or 4 lymphopenia
- Grade 3 or 4 neutropenia that is not associated with fever or systemic infection that improves within 7 days
- Grade 3 thrombocytopenia that is not associated with clinically significant bleeding that requires medical intervention, and improves by at least 1 grade within 3 days
- Isolated Grade 3 electrolyte abnormalities that are not associated with clinical signs or symptoms OR are reversed with appropriate maximal medical intervention within 3 days
- Grade 3 laboratory abnormalities that are responsive to oral supplementation OR deemed by the investigator to be clinically non-significant

A withdrawal or death within the first 2 cycles (42 days) not related to treatment will not be considered a DLT.

DLTs will be counted based on the number of subjects with DLT at a given dose level, not the absolute number of DLTs. No single subject can trigger more than one DLT event.

5.2 Toxicities and Dosing Delays/Dose Modifications

Any patient who receives treatment on this protocol will be evaluable for toxicity. Each patient will be assessed for the development of toxicity according to the Time and Events Table (Section 6.4). Toxicity will be assessed according to the NCI Common Terminology Criteria for Adverse Events (CTCAE), version 5.0. Dose adjustments should be made according to the system showing the greatest degree of toxicity.

5.2.1 IONIS-AR-2.5_{Rx}

IONIS-AR-2.5_{Rx} Dose Modification Levels

Dose reduction levels	Assigned Dose Level = 1	Assigned Dose Level = 2	Assigned Dose Level = 3
Starting Dose	600 mg	750 mg	900 mg
-1	450 mg	600 mg	750 mg
-2	300 mg	450 mg	600 mg
-3	150 mg	300 mg	450 mg

Hematological Toxicities

Hematological Toxicity Dose Reductions for IONIS-AR-2.5 _{Rx} (AR ASO)		
ANC ¹	Platelets	Action
≥ 1,500/µL or 1000-1499/µL or 500-999/µL or	≥100,000/µL 75,000-99,000/µL 50,000-74,000/µL	None. -1 st Occurrence: Hold current dose until ANC ≥ 1,500/µL and platelets ≥ 100,000/µL. Do not replace missed doses. Restart IONIS-AR-2.5 _{Rx} at the next lower dose level as available. -2 nd Occurrence: Hold current dose until ANC ≥ 1,500/µL and platelets ≥ 100,000/µL. Do not replace missed doses. Restart IONIS-AR-2.5 _{Rx} at the next lower dose level as available. -3 rd Occurrence: Hold current dose until ANC ≥ 1,500/µL and platelets ≥ 100,000/µL. Do not replace missed doses. Restart IONIS-AR-2.5 _{Rx} at the next lower dose level as available. -4 th Occurrence: Discontinue protocol therapy. -1 st Occurrence: Hold current dose until ANC ≥ 1,500/µL and platelets ≥ 100,000/µL. Do not replace missed doses. Restart IONIS-AR-2.5 _{Rx} at the next lower dose level as available. -2 nd Occurrence: Hold current dose until ANC ≥ 1,500/µL and platelets ≥ 100,000/µL. Do not replace missed doses. Restart IONIS-AR-2.5 _{Rx} at the next lower dose level as available. -3 rd Occurrence: Hold current dose until ANC ≥ 1,500/µL and platelets ≥ 100,000/µL. Do not replace missed doses. Restart IONIS-AR-2.5 _{Rx} at the next lower dose level as available. -4 th Occurrence: Discontinue protocol therapy.

<500/ μ L or	<50,000/ μ L	
-1st Occurrence: Hold current dose until ANC \geq 1,500/μL and platelets \geq 100,000/μL. Restart IONIS-AR-2.5_{Rx} at the next lower dose level as available.
 
-2nd Occurrence: Hold current dose until ANC \geq 1,500/μL and platelets \geq 100,000/μL. Do not replace missed doses. Restart IONIS-AR-2.5_{Rx} at the next lower dose level as available.
 
-3rd Occurrence: Discontinue protocol therapy.

¹Note: G-CSF (Filgrastim) may be added for low ANC on day of treatment BEFORE a dose reduction is instituted at treating physician's discretions. Neulasta® is NOT allowed.
		

Dose Modifications for Hepatic Toxicity

Patients who develop abnormal liver function tests as defined below, for any reason while on study, will have treatment held and/or reduced according to the following schedules:

HEPATOTOXICITY (BILIRUBIN, SGPT/ALT, SGOT/AST)	
TOTAL BILIRUBIN without ALT/AST increase above baseline value	
Grade 1 (> ULN – 1.5 x ULN)	Maintain IONIS-AR-2.5 _{Rx} level with LFTs monitored bi-weekly.

Grade 2 (> 1.5 – 3.0 x ULN)	Interrupt dosing of IONIS-AR-2.5 _{Rx} . If resolved to \leq grade 1 in \leq 28 days, then reduce by 1 dose level and resume IONIS-AR-2.5 _{Rx} therapy. If toxicity recurs after three dose reductions OR does NOT resolve to \leq grade 1 in \leq 28 days, discontinue IONIS-AR-2.5 _{Rx} therapy.
Grade 3 (> 3.0 – 10.0 x ULN)	Interrupt dosing of IONIS-AR-2.5 _{Rx} . If resolved to \leq grade 1 in \leq 28 days, lower by 1 dose level of IONIS-AR-2.5 _{Rx} . If toxicity does NOT resolve to \leq grade 1 in \leq 28 days or toxicity recurs, discontinue IONIS-AR-2.5 _{Rx}
Grade 4 (> 10.0 x ULN)	Discontinue IONIS-AR-2.5 _{Rx} .
Confounding factors and/or alternative causes for increase of total bilirubin should be excluded before dose interruption/reduction. They include but are not limited to: evidence of obstruction, such as elevated ALP and GGT typical of gall bladder or bile duct disease, hyperbilirubinemia due to the indirect component only (i.e. direct bilirubin component \leq 1 x ULN) due to hemolysis or Gilbert Syndrome, pharmacologic treatment, viral hepatitis, alcoholic or autoimmune hepatitis, other hepatotoxic drugs.	
For patients with Gilbert Syndrome, these dose modifications apply to changes in direct bilirubin only. Bilirubin will be fractionated if elevated.	

AST or ALT	
AST or ALT without bilirubin elevation > 2 x ULN	
Same grade as baseline or increase from baseline grade 0 to grade 1	No dose adjustment required with LFTs monitored weekly if same grade as baseline or bi-weekly in case of increase from baseline grade 0 to 1.

Increase from baseline to grade 2 ($> 3.0 - 5.0 \times \text{ULN}$) OR from baseline grade 2 to grade 3 ($> 5.0 - 20.0 \times \text{ULN}$)	Interrupt dosing of IONIS-AR-2.5 _{Rx} . If resolved to \leq grade 1 in ≤ 28 days, then reduce by one dose level and resume IONIS-AR-2.5 _{Rx} therapy. If toxicity recurs, then reduce by 1 dose level and resume IONIS-AR-2.5 _{Rx} . If toxicity recurs after three dose reductions OR does NOT resolve to \leq grade 1 in ≤ 28 days, discontinue IONIS-AR-2.5 _{Rx} therapy.
Increase from baseline grade 0 or 1 to grade 3 ($> 5.0 - 20.0 \times \text{ULN}$)	Interrupt dosing of IONIS-AR-2.5 _{Rx} until resolved to \leq baseline value, then lower 1 dose level of IONIS-AR-2.5 _{Rx} . If toxicity recurs, discontinue IONIS-AR-2.5 _{Rx} . If toxicity does NOT resolve to \leq baseline value in ≤ 28 days, discontinue IONIS-AR-2.5 _{Rx} therapy.
Grade 4 ($> 20.0 \times \text{ULN}$)	Discontinue IONIS-AR-2.5 _{Rx} .

AST or ALT and concurrent Bilirubin elevation

AST or ALT \geq grade 2 ($> 3 \times \text{ULN}$) in patients with normal values at baseline and total bilirubin $> 2 \times \text{ULN}$ OR AST or ALT \geq grade 3 ($> 5 \times \text{ULN}$) in patients with grade 1 or 2 at baseline, and total bilirubin $> 2 \times \text{ULN}$	Discontinue IONIS-AR-2.5 _{Rx} .
Confounding factors and/or alternative causes for increased transaminases should be excluded before dose interruption/reduction. They include but are not limited to: concomitant medications, herbal preparations or dietary supplements, infection, hepato-biliary disorder or obstruction, new or progressive liver metastasis, and alcohol intake.	

Additional follow-up for hepatic toxicities

Hepatic toxicity monitoring includes the following LFTs: albumin, ALT, AST, total bilirubin (fractionated if total bilirubin $> 2 \times \text{ULN}$), alkaline phosphatase, and GGT. For patients with Gilbert Syndrome: total and direct bilirubin must be monitored, intensified monitoring applies to changes in direct bilirubin only.

Close observation is **recommended** in case of AST, ALT, and/or bilirubin increase requiring dose interruption, which involves:

- Repeating liver enzyme and serum bilirubin tests **two or three times weekly**. Frequency of re- testing can decrease to once a week or less if abnormalities stabilize or return to normal values.
- Obtaining a more detailed history of current symptoms.
- Obtaining a more detailed history of prior and/or concurrent diseases.
- Obtaining a history of concomitant drug use (including non-prescription medications, herbal and dietary supplements), alcohol use, recreational drug use, and special diets.
- Ruling out acute viral hepatitis types A, B, C, D, and E; hepatotropic virus infections (CMV, EBV or HSV); autoimmune or alcoholic hepatitis; NASH; hypoxic/ischemic hepatopathy; and biliary tract disease.

- Obtaining a history of exposure to environmental chemical agents.
- Obtaining additional tests to evaluate liver function, as appropriate (e.g., INR, direct bilirubin).
- Considering gastroenterology or hepatology consultations.
- Assessing cardiovascular dysfunction or impaired liver oxygenation, including hypotension or right heart failure as possible etiologies for liver dysfunction.

Hypersensitivity infusion reaction.

Patients will be monitored for signs and symptoms of infusion-related reactions including rigors, chills, wheezing, pruritus, flushing, rash, hypotension, hypoxemia, and fever. For severe (Grade 3) or life-threatening (Grade 4) infusion-related reactions, stop infusion of IONIS-AR-2.5_{Rx}. Signs and symptoms usually develop during or shortly after drug infusion and generally resolve completely within 24 hours of completion of infusion.

Dose Modifications for other Non-Hematologic Toxicity

- For treatment regimen-related toxicities \geq grade 3 (excluding the hematologic, liver toxicities outlined above, as well as grade 3 nausea/vomiting/diarrhea/fatigue lasting less than 48 hours with optimal medical management, any grade alopecia, or non-clinically significant laboratory abnormalities that resolve within 48 hours with optimal medical management), IONIS-AR-2.5_{Rx} should be withheld until resolution to \leq grade 1 (or to baseline if baseline was greater than grade 1). Treatment may be restarted at next lower dose level if the toxicity improves to grade 1 or lower within 14 days of onset of adverse event. If toxicity recurs at grade 3 or higher, patients will be required to discontinue IONIS-AR-2.5_{Rx} therapy.
- IONIS-AR-2.5_{Rx} treatment days should be skipped for grade 2 related toxicities and restarted at the original dose level once recovered to grade \leq 1. If the same toxicity recurs at grade 2, interrupt IONIS-AR-2.5_{Rx} until recovery to grade \leq 1, then restart IONIS-AR-2.5_{Rx} at the next lower dose level. Discontinue IONIS-AR-2.5_{Rx} therapy IF toxicity recurs after three dose reductions or does not improve to grade 1 or lower within 28 days of onset of adverse event.
- IONIS-AR-2.5_{Rx} should be discontinued for Grade 4 non-hematologic toxicities that are possibly related to the study treatment, unless otherwise specified in the protocol (excluding: grade 4 nausea/vomiting/diarrhea/fatigue lasting less than 48 hours with optimal medical management, any grade alopecia, or non-clinically significant laboratory abnormalities that resolve within 48 hours with optimal medical management).

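### The IONIS-AR-2.5Rx liver dose-modification headings do not fit together: when ALT/AST rises along with bilirubin, the stated bilirubin action can become milder or disappear

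*Combined protocol and SAP*

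**What the plan says.** Section 5.2.1 (Dose Modifications for Hepatic Toxicity) governs IONIS-AR-2.5Rx through three blocks.

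- **Bilirubin table**, headed "TOTAL BILIRUBIN without ALT/AST increase above baseline value". Grade 1 (up to 1.5 x ULN): continue. Grade 2 (above 1.5 to 3 x ULN): interrupt, then resume one level lower. Grade 3 (above 3 to 10 x ULN): the same, with a stricter end point: "28 days or toxicity recurs, discontinue". Grade 4 (above 10 x ULN): discontinue.
- **AST/ALT table**, headed "AST or ALT without bilirubin elevation > 2 x ULN". For an unchanged grade or a change from Grade 0 to 1 the action is "No dose adjustment required with LFTs monitored weekly if same grade as baseline" (bi-weekly monitoring for the 0-to-1 change). Larger rises lead to interruption and reduction, and Grade 4 to discontinuation.
- **Concurrent-elevation row**: discontinue for bilirubin above 2 x ULN with AST/ALT Grade 2 or higher "in patients with normal values at baseline and total bilirubin" above that limit, or with Grade 3 or higher from baseline Grade 1 or 2.

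The same section then gives general rules under the heading "Dose Modifications for other Non-Hematologic Toxicity". Section 5.2 says that the organ system with the worst toxicity drives the adjustment.

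**The concern.** Each of the first two tables is switched off by a change in the other test, and the concurrent row does not pick up everything that is switched off. The result is that a second abnormal liver test can weaken or remove the action that the first would have triggered.

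The switch is easily tripped. Section 9.1 reports ALT/AST increases in the 600 and 900 mg cohorts, mostly Grade 1, and this trial assigns 600, 750 or 900 mg. A Grade 0 to 1 transaminase rise is therefore the drug's documented pattern, and it is enough to take a patient out of the bilirubin table. Baseline Grade 1, needed for the 1-to-2 gap, is also possible, because eligibility allows AST/ALT up to 2.5 x ULN (Section 3.1.10).

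At stake is whether two centers hold and reduce the study drug in the same way, and as the sponsor presumably intended, when both tests move. The closer liver follow-up in Section 5.2.1 is tied to increases that require interruption, so that prompt is lost wherever no row requires one.

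**Working it through.** The plan gives no figure to reproduce. The check is to apply the three blocks literally to every combination.

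**Grid.** ALT/AST grade increases from baseline 0, 1 or 2: 0 to 1–4 (4), 1 to 2–4 (3), 2 to 3–4 (2), which makes 9. Bilirubin bands (x ULN), cut at the limits used in the tables: 6. Total 9 x 6 = 54 combinations. These are rule combinations, not patient frequencies.

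I = interrupt, then reduce; D = discontinue.

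| ALT/AST grade | ≤1 | >1–1.5 | >1.5–2 | >2–3 | >3–10 | >10 |
|---|---|---|---|---|---|---|
| Not above baseline: bilirubin table alone | – | continue | I | I | I | D |
| 0 to 1 | no change | no change | **no change** | **no row** | **no row** | **no row** |
| 0 to 2 | I | I | I | D | D | D |
| 0 to 3 | I | I | I | D | D | D |
| 0 to 4 | D | D | D | D | D | D |
| 1 to 2 | I | I | I | **no row** | **no row** | **no row** |
| 1 to 3 | I | I | I | D | D | D |
| 1 to 4 | D | D | D | D | D | D |
| 2 to 3 | I | I | I | D | D | D |
| 2 to 4 | D | D | D | D | D | D |

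**Result.**

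- (a) In the >1.5–2 band, 1 of 9 grade changes (0 to 1) gets a milder action than bilirubin alone.
- (b) Above 2 x ULN, 2 changes x 3 bands = 6 of 27 combinations match no liver row. With ALT/AST Grade 1 to 2 and bilirubin 2.5 x ULN, each abnormality alone would require interruption and reduction. At bilirubin above 10 x ULN, bilirubin alone would require discontinuation.
- Together, 7 of 54.

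Rises in ALT/AST within the baseline grade also leave the bilirubin table. They are often trivial and are not counted.

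**If the general rules fill the gaps.** The Grade 2 bullet has no liver exclusion, and the Grade 3 bullet excludes only what the tables cover ("excluding the hematologic, liver toxicities outlined above").

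- *Grade 2 bilirubin, 3 combinations (1 in a, 2 in b).* Dosing is held for related events, but the first restart is at the original dose. The missed reduction is 900 to 750 mg (150/900 = 17%), 750 to 600 mg (150/750 = 20%) or 600 to 450 mg (150/600 = 25%).
- *Grade 3 bilirubin, 2 combinations.* The limit for recovery is stricter (14 against 28 days). Recurrence is looser: discontinuation only at Grade 3 or higher, against any recurrence in the bilirubin row.
- *Grade 3 and 4 bilirubin, 4 combinations.* The general rules also exempt "non-clinically significant laboratory abnormalities that resolve within 48 hours with optimal medical management" and apply only to treatment-related events. The liver tables have no such exemption, although they too ask that other causes be excluded first.

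**How many patients.** The documents give no bilirubin rate for the combination. At enzalutamide's any-grade rate of 3% (Section 1.4), 35 x 0.03 = 1.05 patients would have any rise. At an assumed 10%, 35 x 0.10 = 3.5. Those with bilirubin above 1.5 x ULN and a small ALT/AST rise as well would be fewer.

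**The case against.** The strongest reply is that the intent is clear and other rules stand behind the tables.

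- *No liver row is not the same as no rule.* A combination that the liver tables do not cover can be read as falling under the general rules, which hold or stop dosing for related events. This reading is fair, but their heading limits them to other toxicity, and in zone (a) they contradict the row that requires no change. Even if they apply, the first-restart reduction after Grade 2 bilirubin is lost.
- *The no-change row concerns transaminases only.* Probably so. It already overlaps the bilirubin table when ALT/AST is unchanged, which suggests that the rows were not written to exclude one another. But then zone (a) has no liver action for the bilirubin at all.
- *The worst toxicity governs.* Section 5.2 compares organ systems. It does not choose between two tables for the same organ.
- *An investigator would apply the bilirubin rows anyway.* That is likely, and on that reading nothing is lost. It shows what was meant, but the heading says otherwise.
- *Enzalutamide is held.* Section 5.2.2 does this for related bilirubin of Grade 2 or higher. It does not govern the investigational drug.
- *The consequences are small.* This stands. The documented liver signal is transaminases, no bilirubin elevation is reported with this drug, and isolated ALT/AST rises are covered. It limits the severity without removing the inconsistency.

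**Conclusion.** The concern holds. As written, a safety rule for the study drug becomes milder in 1 combination and silent in 6, out of 54, when a second liver test worsens. If the general rules are taken to fill both zones, the hold for related Grade 2 bilirubin survives and the one-level reduction at first restart is lost. On the literal reading of zone (a), the hold is lost as well.

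This is a minor-to-moderate error that should be fixed. The count rests on a literal reading of the headings and on ALT/AST grade changes only. The expectation of few affected patients rests on the enzalutamide rate or the assumed 10%. The dose-finding model, PSA endpoint and success rule do not use these tables, so the MTD estimate and the efficacy conclusion are not affected.

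**What to change.** In the next amendment to Section 5.2.1:

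1. Remove the ALT/AST condition from the heading of the bilirubin table.
2. Replace the bilirubin condition in the AST/ALT heading with a statement that both tables apply whenever the concurrent-elevation row is not met.
3. Add one sentence: when both tables apply, take the stricter action.

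On the 54-combination grid this changes the dosing action in the 7 faulty combinations and in no others. None is left unmatched, and none is milder than either abnormality alone. Outside that grid, it also returns within-grade ALT/AST rises to the bilirubin table. For example, bilirubin 1.7 x ULN with a trivial ALT rise would then lead to interruption, as the same bilirubin already does with ALT/AST unchanged. The sponsor should confirm that this is wanted.

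The cost is two headings and one sentence. No new tests are needed: the metabolic panel in Section 6.0 already includes ALT, AST and total bilirubin at every dosing visit.
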